6.4 Study specific tolerance for inclusion/exclusion criteria

Subjects who fail to meet one or more of the inclusion criteria or meet any of the exclusion criteria will not be enrolled in this study. Waivers of any of the above study entry criteria will not be granted.

7. CONCURRENT MEDICATIONS

All subjects who are treated for acute pulmonary exacerbations are treated with antibiotic combinations, utilizing a minimum of 2 agents. Intravenous tobramycin and intravenous colistin are never utilized simultaneously, due to their combined nephrotoxicity. Thus, the choice of accompanying antibiotics will be made by the subject's treating physician. Subjects will only be randomized to either tobramycin or colistin.

7.1 Allowed medications and treatments

Standard therapy for CF APE is allowed. Subjects will receive nebulized bronchodilators, mucolytics, airway clearance treatments, nutritional support, diabetes management, and pancreatic enzymes, based on current standard recommendations for CF exacerbation treatment.

8. STUDY TREATMENTS

8.1 Method of assigning subjects to treatment groups

All subjects will enter the study at the time they are diagnosed with an APE and designated for hospital admission to treat with a drug regimen which includes either intravenous tobramycin or colistin. Block randomization will be utilized based on gender, FEV₁% predicted, and time of enrollment to ensure relatively equal treatment allocation based on these variables.

8.2 Blinding

Subjects and investigators will not be blinded to the use of tobramycin versus colistin. Measurement of tobramycin pharmacokinetics and adjustment of doses appropriately is standard clinical practice and cannot be modified for the study.

8.3 Packaging and labeling of study drugs to site

Intravenous tobramycin (X-gen Pharmaceuticals) and intravenous colistin (Perrigo Company), which are administered to patients with CF APE, are purchased and formulated as solutions for intravenous administration by the Pharmacy Department at

National Jewish Health | Saint Joseph Hospital. There will be no change to the formulation or supplier of these products from current standard practice. The central study pharmacy is synonymous with National Jewish Health | Saint Joseph Hospital's inpatient pharmacy.

8.4 Handling and dosing regimens for study drugs.

8.4.1 Pre-treatment hydration: On the date of admission, all subjects will receive an initial normal saline (NS) 1 liter bolus. All subjects are initiated on the non-nephrotoxic component of their APE treatment on admission day one, as directed by their treating physician (beta lactam, carbapenem, monobactam, etc), based on infecting pathogen profile, previous treatment response, antimicrobial resistance, and drug allergies ³⁰⁻³². On the second hospital day, once a baseline serum creatinine (SCr) has been confirmed and the patients' attending physician and clinical pharmacist assess that they are ready to initiate treatment with either tobramycin or colistin, one of the three treatment arms will be implemented as directed by randomization. As per institutional protocol, all subjects receiving tobramycin or colistin receive 1 liter NS IV daily.

8.4.2 Specific drug treatment arms

Standard colistin arm: Subjects initially receive IV colistin 2.5 mg/kg/d divided into three times daily (TID) dosing (Perrigo Company) ^{1,15, 24}. Previous literature has supported upward dose titration to minimize the incidence of side effects associated with parenteral administration¹⁵. Subjects receiving colistin will undergo a 2 day up-titration of dose to an ultimate dose of 4-5 mg/kg/day, for a total treatment of 14 days¹⁵. The drug is infused over 30 minutes on a TID dosing schedule. There are no pharmacokinetic measurements to guide standard dosing; however, plasma, sputum, and urine will be collected and analyzed from the subjects in this treatment arm on the same schedule as the modified colistin arm to serve as study controls. Treatment is currently guided by evidence of neurotoxicity or nephrotoxicity, based on clinical exam and on serum and urine studies.

Modified colistin arm Subjects receiving IV colistin undergo a 2 day up-titration to a maximum dose of 5 mg/kg/day, divided into twice daily (BID) dosing, for a total treatment of 14 days. The drug is infused over 30 minutes BID. Steady state plasma concentrations on visit 2 (generally at the 2nd-3rd dose once at goal dosing) will be measured; specifically, colistin peak (30-60 minutes after infusion), midpoint (4-6 hours after infusion) and/or trough (30-0 minutes prior to next infusion). A steady state sputum sample will be procured at visit 2 to assess epithelial lining concentrations, unless subjects are on inhaled colistin as this will create inaccuracies in colistin sputum concentration measurements. Processing of sputum for colistin measurements will be performed by the standardized method for processing sputum developed by CF Therapeutic Development Network ^{33,34}. A baseline and steady state urine samples will also be collected. Levels of colistin A and B and pro-drug from plasma, sputum, and urine (following processing) will be quantified within 36 hours to allow for measurement and interpretation. [name] will determine the optimal dose and intervals for APE subjects based on PK modeling with feedback from the PI, treating physician, and the National Jewish Health | Saint Joseph Hospital inpatient pharmacists. Colistin concentrations in plasma, sputum, and urine will be re-assessed at visit 3, after PK adjusted optimal dosing of colistin has reached a steady state.

Standard tobramycin arm: Subjects receive IV tobramycin 8-10 mg/kg/day (X-gen Pharmaceuticals) with once daily dosing for 14 days. Peaks and troughs are drawn with the second dose of tobramycin, and the drug is infused over 30 minutes. Dose adjustment will occur to achieve non-detectable troughs and peaks 20-30 mg/dL². Tobramycin concentrations are assessed once weekly during each week of APE treatment.

8.4.3 Dose modification: Subjects active in the study who experience moderate to severe toxicity will undergo dose adjustments as follows. If clinical providers and site investigators believe that it is appropriate to have the subject continue in the study, this will be allowed. If study drug is discontinued, the data acquired prior to its discontinuation will be utilized in the analysis.

1. Tobramycin will be discontinued if ototoxicity occurs (patient complains of ringing in ears and/or hearing loss).
2. Tobramycin will be held with increases of creatinine >0.3 mg/dL. If creatinine increases are not reversible, the drug is discontinued. If they are reversible, the drug may be resumed at lower dosing or longer intervals, at the discretion of the physician and the clinical pharmacist in joint consultation.
3. Colistin will be discontinued for serious episodes of neurotoxicity, such as debilitating headache, seizure, and neuromuscular weakness.
4. Colistin will be held for one dose and then resumed at a lower dose if creatinine rises \geq 0.3 mg/dL from baseline. If creatinine fails to recover or continues to rise, the drug will be discontinued. Patients who do not undergo PK measurements are maintained at the highest dose achievable (between 3-5 mg/kg/day) without renal insufficiency (< 0.3 mg/dL increase in serum creatinine).

8.4.4 Study drug preparation, handling and dispensing: Appropriately trained pharmacy personnel and nursing staff are responsible for the administration of medications. Medications are dispensed and labeled in accordance with federal and local state Board of Pharmacy regulations.

8.4.5 Administration instructions: Instruction of hours of administration, dose, and duration of administration will be transmitted from the National Jewish Health | Saint Joseph Hospital inpatient pharmacists to CF pulmonary floor nursing staff. Drugs will be administered through indwelling peripherally inserted central catheters (PICC) or indwelling ports.

8.4.6 Storage: All study drugs are stored in the National Jewish Health | Saint Joseph Hospital's inpatient pharmacy in a secure area under restricted access at controlled room temperatures, as recommended by the product manufacturer.

8.5 Study Drug Accountability: Subjects will be dispensed study drugs during the time of their inpatient admission and all infusions will be recorded by nursing staff into the electronic medical record. Additionally, the dose and duration of dosing for each subject will be recorded with each subject ID.

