steady state serum samples was performed, in addition to PD modeling of the area under the curve to minimum inhibitory concentration (AUC₀₋₂₄:MIC) of the bacteria. The AUC: MIC is a better predictor of successful outcomes in *P. aeruginosa* treatment, with optimal efficacy occurring at ratios >60^{25,26}.

Colistin PK/PD analysis of standard colistin dosing. Active colistin components were combined for PK/PD analysis. The mean \pm SD colistin Cmax, Cmin, half-life, VD, CL, and AUC₀₋₈ were 1.1 ± 0.7 mg/L, 0.5 ± 0.5 mg/L, 5.7 ± 2.0 hours, 226 ± 220 L, 30.5 ± 32.6 L/hr and 3.8 ± 3.1 mg*hr/L, respectively. Monte Carlo simulations were conducted to determine the dosing models required to achieve AUC/MIC ratios between 48-60, as these cut points have demonstrated 1-2 log kill in murine models of thigh and pulmonary infections (Table 2)^{25,26}. MIC values were obtained from historical Colorado Adult Program CF patients' microbiology culture data. Seventy percent of isolates had MICs ranging from 0.12- 1.0. Different dosing strategies were employed until >80% and >90% target attainment was achieved at an AUC/MIC ratio >60. Total daily colistin dosages required to achieve pharmacodynamics targets are illustrated in Table 2. Based on MIC distributions, our PD model suggests that the average daily dosing achieved in the pilot study (3.4 mg/kg/day) is effective at achieving PD targets in approximately 25% of isolates in the first week of therapy. Higher daily dosages of colistin are required to achieve therapeutic targets. We estimate that doses of 5 mg/kg/day are more optimal and within the realm of achievable dosing without increasing toxicity.

Table 2: Probability of achieving pharmacodynamics targets (AUC/MIC > 60) with varying colistin dosing strategies in patients with normal renal function.

MIC	0.06	0.12	0.25	0.5	1
6.85 mg/kg/d	100.0	85.3	38.8	15.0	4.7
5 mg/kg/d	100.0	64.9	23.4	8.5	1.3
3.42 mg/kg/d	100.0	41.8	12.9	4.7	0.0
3 mg/kg/d	77.8	33.4	11.6	1.7	0.0

(data are presented as percentages)

As an additional consideration, a concentration curve (Figure 3) demonstrates that many subjects had detectable colistin prodrug in the plasma at the end of the dosing interval, indicating significant accumulation and potentially increasing toxicity to patients. Thus, higher dosing at less frequent intervals appears to be a reasonable approach to optimizing attainment.

[figure not shown]

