8.7 Standard of care treatment with tobramycin

Subjects will receive intravenous tobramycin in accordance with standard procedures established through the Department of Pharmacy and Department of Nursing at National Jewish Health | Saint Joseph Hospital. It is administered through a peripheral IV, peripherally inserted central catheter (PICC line), or indwelling port.

8.7.1 Administration instructions: Intravenous tobramycin will be administered as per standard care³⁵ on a weight-based dosing regimen. The amount to be given to each patient who is prescribed tobramycin is based on standard treatment recommendations of 8-10 mg/kg/day as a one time dose daily. The precise dose is determined by the CF clinical pharmacist and treating physician, based on previous experiences with dosing of the drug and previous doses which achieved levels within treatment guidelines for that individual. Precise administration instructions are as follows:

Tobramycin (X-gen Pharmaceuticals) is reconstituted in a 1.2 gram vial with 30 cc of sterile water for injection with resultant solution of 40 mg/ml. The appropriate dose is drawn up in a syringe and injected into 100 ml normal saline piggy back. The medication is infused over 30 min. Tobramycin peaks and troughs are drawn with the second dose of tobramycin. Dose adjustment will occur to achieve non-detectable troughs, and peaks 20-30 mg/dL². Tobramycin concentrations are assessed once weekly during each week of APE treatment.

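### The tobramycin peak target is written in mg/dL in both dosing sections, which puts it at 200-300 mg/L, out of reach of 8-10 mg/kg unless the volume is 0.050 L/kg or less; mg/L was probably meant.

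*Combined protocol and SAP*

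**What the plan says.** The tobramycin target appears twice, with the same numbers and unit:

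- Section 8.4.2, standard tobramycin arm: "Dose adjustment will occur to achieve non-detectable troughs and peaks 20-30 mg/dL".
- Section 8.7.1, administration instructions: "Dose adjustment will occur to achieve non-detectable troughs, and peaks 20-30 mg/dL".

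The digit 2 that follows the unit in the text is a citation number, pointing to the randomised trial of once versus three-times daily tobramycin. It is not part of the unit. The dose in 8.7.1 follows "standard treatment recommendations of 8-10 mg/kg/day as a one time dose daily", infused over 30 minutes.

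No other section states the peak target in a different unit. Section 4.1 (tobramycin dose adjustment) and section 9.2.3 (tobramycin pharmacokinetic measurements) give no numeric target at all.

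Elsewhere the protocol reports drug concentrations in mg/L. In the pilot data of section 1.1, colistin Cmax, Cmin and half-life "were 1.1 ± 0.7 mg/L, 0.5 ± 0.5 mg/L, 5.7 ± 2.0 hours". The unit mg/dL is used for serum creatinine, including in section 8.4.3, directly after the first statement of the tobramycin target.

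**The concern.** A target of 20-30 mg/dL is ten times a target of 20-30 mg/L, and the stated dose does not look able to produce it. If the written unit is wrong, the error sits in the operative dosing rule of the comparator arm.

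Acute kidney injury is part of the primary safety endpoints (section 5.1), and the protocol treats tobramycin as nephrotoxic; section 7 says "Intravenous tobramycin and intravenous colistin are never utilized simultaneously, due to their combined nephrotoxicity". Read literally, at any volume above 0.050 L/kg every peak on 8-10 mg/kg falls below target, so the peak half of the rule would favour raising the dose. A reader relying on the document could not tell which concentration the arm was meant to reach.

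**Working it through.** **Inputs from the protocol**

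| Input | Value | Where |
|---|---|---|
| Peak target | 20-30 mg/dL | 8.4.2 and 8.7.1 |
| Dose | 8-10 mg/kg, once daily | 8.4.2 and 8.7.1 |
| Infusion time | 30 minutes | 8.4.2 and 8.7.1 |
| Trough target | not detectable | 8.4.2 and 8.7.1 |
| Tobramycin volume of distribution | not given | none |

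The protocol does not derive the target, so there is no calculation of its own to reproduce. The check is whether the dose and the target can both hold.

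**Step 1: convert the unit.** 1 mg/dL = 10 mg/L, so 20-30 mg/dL = 200-300 mg/L.

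**Step 2: find the volume the written target requires.** With no carry-over, and in a one-compartment model, peak ≤ dose / V, so V ≤ dose / peak.

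| Dose | Peak 200 mg/L | Peak 300 mg/L |
|---|---|---|
| 8 mg/kg | 8/200 = 0.040 L/kg | 8/300 = 0.027 L/kg |
| 10 mg/kg | 10/200 = 0.050 L/kg | 10/300 = 0.033 L/kg |

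The largest volume compatible with any part of the written target is 0.050 L/kg. This step uses only the protocol's dose, target and trough condition.

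**Step 3: allow for the infusion and residual accumulation.** With k = ln 2 / half-life and T = 0.5 h, the peak is multiplied by (1 − exp(−kT)) / (kT) and by 1 / (1 − exp(−24k)). The half-lives are assumed. At 10 mg/kg and 200 mg/L:

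- Half-life 1 h: 0.050 × 0.845 × 1.000 = 0.042 L/kg.
- Half-life 4 h: 0.050 × 0.958 × 1.016 = 0.049 L/kg.

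So 0.050 L/kg is a slightly generous bound in this model.

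**Step 4: peaks at assumed volumes.**

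| Assumed V | Lowest peak | Highest peak | Shortfall against 200-300 mg/L |
|---|---|---|---|
| 0.2-0.4 L/kg | 8/0.4 = 20 mg/L | 10/0.2 = 50 mg/L | 200/50 = 4 to 300/20 = 15 times |
| 0.1-0.6 L/kg | 8/0.6 = 13.3 mg/L | 10/0.1 = 100 mg/L | 200/100 = 2 to 300/13.3 = 22.5 times |

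**Step 5: dose needed at 0.2-0.4 L/kg.**

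- For 200-300 mg/L: 200 × 0.2 = 40 to 300 × 0.4 = 120 mg/kg, which is 40/10 = 4 to 120/8 = 15 times the stated dose.
- For 20-30 mg/L: 20 × 0.2 = 4 to 30 × 0.4 = 12 mg/kg, which brackets 8-10 mg/kg.

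**Step 6: does mg/L fit better?** With a target of 20-30 mg/L:

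- Part of the 8-10 mg/kg range meets it for V from 8/30 = 0.27 to 10/20 = 0.50 L/kg.
- The whole dose range meets it for V from 10/30 = 0.33 to 8/20 = 0.40 L/kg.
- At V = 0.2 L/kg the doses give 8/0.2 = 40 to 10/0.2 = 50 mg/L, above the target.

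So mg/L is consistent with the stated dose over a broad range of volumes, though not at every assumed one.

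**The case against.** The strongest case against is that the written figure does not drive what happens to patients. Section 4.1 has the investigator and treating physician adjust tobramycin by CF treatment guidelines with the inpatient pharmacists. Section 8.7.1 bases the individual dose on "previous doses which achieved levels within treatment guidelines for that individual". Section 8.2 adds: "Measurement of tobramycin pharmacokinetics and adjustment of doses appropriately is standard clinical practice and cannot be modified for the study". Section 8.4.3 provides a stop: "Tobramycin will be held with increases of creatinine >0.3 mg/dL". The same target sentence also demands undetectable troughs, which restrains escalation. Taken literally, the rule is more likely to prompt a query than a tenfold overdose. All of this stands, and it keeps the point minor. It does not make the written target attainable.

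A second objection is that the documents give no tobramycin volume, so calling 0.027-0.050 L/kg implausible rests on assumption, as do the shortfall multiples. That is correct. The conversion and the implied volume follow from the protocol; the multiples hold only over the ranges shown. The intended unit is likewise an inference.

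A third is technical. The protocol gives no sampling time for the tobramycin peak, whereas section 8.4.2 gives 30-60 minutes after infusion for colistin. A sample drawn before distribution is complete can exceed dose / V when V is a steady-state volume, so the bound is not absolute. At 0.2-0.4 L/kg, however, the reading would have to be at least four times dose / V to touch the bottom of the written range.

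**Conclusion.** The concern holds, as a minor point. As written, the tobramycin peak target is 200-300 mg/L, which 8-10 mg/kg once daily can reach only at an apparent volume of 0.050 L/kg or less. That bound assumes negligible carry-over and one-compartment behaviour. The size of the miss (4 to 15 times at 0.2-0.4 L/kg, 2 to 22.5 times at 0.1-0.6 L/kg) depends on volumes the documents do not supply.

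Confidence is high that the unit as written does not fit the dose. That mg/L was meant is likely but unconfirmed. It is supported by the fit with the stated dose and by the use of mg/L for colistin levels.

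No effect on power, alpha or the primary analysis is claimed. Nor is any effect claimed on time to therapeutic dosing, because nothing in the documents defines therapeutic tobramycin dosing by this range.

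**What to change.** Change mg/dL to mg/L (equivalently mcg/mL) for the tobramycin peak in sections 8.4.2 and 8.7.1. First confirm the unit against the source cited for the target and against the reporting unit of the hospital laboratory that measures the levels (section 9.2.3).

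The cost is one unit corrected in two places. Design, endpoints, analysis, sample size and study procedures stay as they are.

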Safety analysis: The safety profile of each colistin arm and the tobramycin arm will be assessed in terms of the following: incidence of AKI, incidence of treatment related clinical events (ototoxicity, vestibular toxicity, and neurotoxicity). Adverse event rates will be compared between treatment groups using logistic regression, adjusting for age, medications such as vancomycin, baseline FEV₁, admits in the previous year, exposure to nephrotoxic antibiotics in the previous 5 years, and diagnosis of CF related diabetes (CFRD) as covariates. Repeated measures within subjects will be accounted for by including a random intercept for subjects.

Summary statistics and changes from admission will be presented for serum Cr and urine:protein ratios. The urine protein:creatinine ratio will be assessed as a biomarker of drug toxicity. We will analyze Nephrocheck® assay results in a case control design. Subjects who develop AKI within each of the study arms will have urine thawed and analyzed by Nephrocheck® and those results will be compared to age, gender, and FEV₁, matched control urines obtained from subjects

	within the study who did not develop AKI. An adjusted odds ratio will be derived from a model fitted with unconditional logistic regression and adjusted for confounding variables. Estimates of odds ratios and 99% confidence intervals will be presented.
RATIONALE FOR NUMBER OF SUBJECTS	In a retrospective cohort 500 subjects, FEV1% improvement after tobramycin treatment during exacerbation therapy was 3% higher than in those receiving colistin; however, rates of acute kidney injury (rise in serum creatinine ≥ 0.3 mg/dL while on therapy) were 60% higher in tobramycin treated subjects versus standard colistin treated subjects. Since no preliminary data was available on less frequent colistin dosing, which theoretically would lead to less frequent episodes of kidney injury, we estimate we are powered to identify a safer method for dosing colistin with samples of 30 subjects per group, though we may be underpowered to find a significant FEV ₁ difference between groups.

Title: IV Colistin for Pulmonary Exacerbations: Improving Safety and Efficacy

1. Background

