Retrospective efficacy and safety of standard IV colistin dosing in a large CF inpatient population. We retrospectively analyzed IV antibiotic courses for treatment of CF APE amongst patients of the Denver Adult CF Program from 2012-2015. Greater than 240 courses of colistin were administered to 240 adult subjects, and >350 courses of tobramycin in 350 subjects. A dataset of admissions with complete data (n=465) was analyzed for FEV₁ improvement based on treatment with tobramycin or colistin and for the development of acute kidney injury (AKI) based on an absolute increase of serum creatinine by ≥ 0.3 mg/dl²⁷. Subjects received on average a course of 14.6 days of colistin during APE treatment versus 12.7 days of tobramycin. The average ages of subjects receiving tobramycin and colistin were 31 and 32 years old respectively. The tobramycin group was 57% female, while the colistin group was 60% female. The colistin group consisted of 66% CFRD diagnosed patients, while the tobramycin group had 38% with CFRD. More admissions occurred for the colistin group (average of 2.3/year), versus the tobramycin group, which underwent an average of 1.8 admits per year. Pre-treatment FEV₁ % predicted ranged higher for the group receiving tobramycin (average of 50%), versus the colistin group (average of 40% predicted), reflecting a sicker population receiving intravenous colistin. Of interest, the degree of FEV₁ improvement before and after APE treatment was 12% predicted with tobramycin versus 9% predicted for colistin (p=0.006). However, the small increase in FEV₁ improvement came at a price, since the incidence of AKI was 19% for the tobramycin group and 12% for the colistin group, giving an OR of 3.6 for tobramycin (p=0.002). The analysis was adjusted for prior year admissions, reflecting the reality that CF subjects receive multiple IV antibiotic courses over sequential years. Since mounting evidence

demonstrates that AKI occurrences, defined as a creatinine rise by ≥ 0.3 mg/dL, are associated with increased morbidity, higher one year mortality, and chronic kidney disease, the fact that patients experience this endpoint not infrequently, and repeatedly, is meaningful^{28,29}.

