9.3.2 Nephrotoxic Acute Kidney Injury assay (urine)

Urine will be obtained as noted in the Schedule of Events and will undergo cryopreservation. In patients who develop acute kidney injury (elevation of serum creatinine ≥ 0.3 mg/dL) urine will be thawed and evaluated for neutrophil gelatinase-associated lipocalin (NGAL) and tissue-inhibitor of metalloproteinase 2 (TIMP-2) and insulin-like growth factor binding protein 7 (IGFBP-7). NGAL will be evaluated by enzyme-linked immunosorbent assay (ELISA). TIMP-2 and IGFBP-7 will be measured by the Nephrocheck® assay. Nephrocheck® is a newly FDA approved assay for detection of nephrotoxic acute kidney injury and will be tested for its sensitivity and specificity for detection of acute kidney injury in CF within the study. Both assays will be run by the University of Colorado Renal Division.

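### The tobramycin hold starts above a 0.3 mg/dL creatinine rise, while the colistin hold and the AKI threshold start at 0.3 mg/dL

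*Combined protocol and SAP*

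**What the plan says.** Section 8.4.3 (Dose modification) sets the creatinine rules for both drugs in one numbered list.

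- Item 2: "Tobramycin will be held with increases of creatinine >0.3 mg/dL". The item does not name the reference value for the increase.
- Item 4: "Colistin will be held for one dose and then resumed at a lower dose if creatinine rises" by 0.3 mg/dL or more from baseline. The last sentence of the item keeps colistin subjects without PK measurements at the highest achievable dose "without renal insufficiency (< 0.3 mg/dL increase in serum creatinine"). A rise of exactly 0.3 mg/dL is thus already outside the tolerated range.

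The AKI threshold appears in four places, each time with 0.3 mg/dL included:

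- Section 9.3.2, for the trial itself: "In patients who develop acute kidney injury (elevation of serum creatinine ≥ 0.3 mg/dL) urine will be thawed".
- Section 1.1, for the retrospective cohort, citing the KDIGO reference: "absolute increase of serum creatinine by ≥ 0.3 mg/dl".
- The synopsis (rationale for number of subjects) and section 15.4, again for the retrospective cohort: "rates of acute kidney injury (rise in serum creatinine ≥ 0.3 mg/dL while on therapy) were 60% higher in tobramycin treated subjects".

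The primary safety endpoint in section 5.1 refers to KDIGO criteria without giving a number.

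**The concern.** A hold rule tells ward staff what they must do on a given laboratory result, so its boundary should be clear and should match the harm it guards against. As written, a tobramycin subject can reach the trial's AKI threshold without triggering the tobramycin hold, whereas the same result in a colistin subject triggers one. The later trigger applies to the drug with the higher AKI rate in the sponsor's own retrospective data: in section 1.1 "the incidence of AKI was 19% for the tobramycin group", against 12% for colistin. Section 1.1 also links rises of this size to morbidity, one-year mortality and chronic kidney disease. No section gives a reason for a different tobramycin boundary.

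**Working it through.** No stated sample size or power figure bears on this point. The check sets the three rules side by side at and around the boundary.

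| Creatinine rise | AKI threshold (9.3.2) | Colistin hold (8.4.3 item 4) | Mandated tobramycin hold (8.4.3 item 2) |
|---|---|---|---|
| below 0.3 mg/dL | no | no | no |
| exactly 0.3 mg/dL | yes | yes | **no** |
| above 0.3 mg/dL | yes | yes | yes |

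The rules part only at exactly 0.3 mg/dL.

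**Effective trigger.** The documents do not state how finely creatinine is reported, so two assumed steps are shown:

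- Step of 0.1 mg/dL: the first value above 0.3 is 0.3 + 0.1 = 0.4 mg/dL, so the mandated tobramycin hold starts at 0.4.
- Step of 0.01 mg/dL: the first value above 0.3 is 0.3 + 0.01 = 0.31 mg/dL, so it starts at 0.31.

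**Number of subjects, context only.** Inputs are 30 subjects per group (section 15.4) and the retrospective tobramycin AKI rate of 19% (section 1.1):

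30 × 0.19 = 5.7 subjects expected to reach 0.3 mg/dL or more.

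The share at exactly 0.3 cannot be computed without the reporting step and the distribution of rises; it could be anything from none to all. The 5.7 is neither an estimate of those affected nor an upper limit on them. The trial's AKI rate may differ, and so may the size of the tobramycin arm, because section 6.2 randomizes subjects who cannot take tobramycin to the two colistin arms only.

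**Endpoints.** A rise of 0.3 mg/dL meets the AKI threshold in every arm whether or not the drug is held, so the AKI count does not change. Secondary endpoint 1 (therapy interruptions due to creatinine) does depend on the hold rules. However, those rules and the dosing frequencies differ between the drugs in larger ways, so no direction of bias is claimed.

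**Reference value.** Item 2 omits the baseline that item 4 names. This is a wording point only, since three sections make baseline the natural reading. Section 8.4.1 starts the study drug "once a baseline serum creatinine (SCr) has been confirmed", section 10.1 records it, and section 10.5 follows renal toxicity until creatinine returns to it.

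**The case against.** The strongest reply is that this is an editorial slip with almost no consequence.

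- **The signs may be used interchangeably.** Section 1.1 reports the same two pilot subjects with an inclusive sign in the text and a strict sign in Table 1. A bar lost when the PDF was read is also possible. The slip is plausible. The lost bar cannot be excluded, but the inclusive sign survived in item 4 of the same list. On either explanation, the current text has no correction of item 2.
- **The AKI threshold is thinly stated for the trial.** Most of the citations describe the retrospective cohort, and the primary endpoint gives no number. That is fair. Section 9.3.2 does state the cut for trial subjects, and section 1.1 ties it to the KDIGO reference that the endpoint invokes. The mismatch between items 2 and 4 stands without any of this.
- **Clinicians can act anyway.** Creatinine is drawn daily, tobramycin levels are monitored, and the physician and pharmacists adjust doses. An unmanaged rise in an inpatient is unlikely. None of these provisions makes a hold mandatory at 0.3 mg/dL, however, and the discretion written into item 2 concerns resuming the drug after a reversible rise.
- **The tobramycin rule is not laxer overall.** Once triggered, colistin misses one dose and resumes at a lower dose, while tobramycin stops if the rise is not reversible and otherwise may be resumed after joint consultation. This is correct, and the criticism is confined to the trigger.
- **Tobramycin management is standard care.** Section 8.2 says so for pharmacokinetic measurement and dose adjustment. It gives no creatinine threshold and so does not justify a different boundary.

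What survives of the reply is that the effect is small and the cause may be clerical.

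**Conclusion.** The inconsistency is present in the current text, and it is minor. At a rise of exactly 0.3 mg/dL the protocol mandates a hold for colistin but not for tobramycin, although that value meets the stated AKI threshold. No error in AKI counts and no direction of bias in the interruption endpoint follows from it. How often it would matter is unknown and depends on the reporting precision of creatinine. The conclusion assumes that the strict sign in item 2 is what the protocol prints, and that the cut in section 9.3.2 is the one meant by the reference to KDIGO criteria. If the second assumption failed, the difference between the two hold rules would remain.

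**What to change.** Reword section 8.4.3 item 2 to: *Tobramycin will be held if creatinine rises ≥0.3 mg/dL from baseline*, with baseline defined as the value confirmed before dosing under section 8.4.1. This brings both hold rules and the AKI threshold to the same boundary and supplies the missing reference value. If a later trigger for tobramycin is intended, the protocol should say so and give the reason.

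The cost is one line of text, submitted as an amendment under section 17.1. Baseline creatinine is already confirmed before the study drug starts and creatinine is already drawn daily, so no new data, visit or analysis is needed, and the sample size is unchanged.
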